#### **Variables**

The following variables will be collected in the CRF for each AE:

- AE (verbatim)
- The date when the AE started and stopped
- CTCAE grade
- Whether the AE is serious or not
- Investigator causality rating against the MEDI-573 (yes or no)
- Action taken with regard to MEDI-573
- Outcome

For SAEs additional variables will be collected including treatment given for the event.

Date

It is important to distinguish between serious and severe AEs. Severity is a measure of intensity whereas seriousness is defined by the criteria in Section 6.4.2. An AE of severe intensity need not necessarily be considered serious. For example, nausea that persists for several hours may be considered severe nausea, but not a SAE. On the other hand, a stroke that results in only a limited degree of disability may be considered a mild stroke but would be a SAE.

The grading scales found in the revised NCI CTCAE version 4.0 will be utilised for all events with an assigned CTCAE grading. For those events without assigned CTCAE grades, the recommendation in the CTCAE criteria that converts mild, moderate and severe events into CTCAE grades should be used.

### **Causality collection**

The investigator will assess causal relationship between MEDI-573 and each AE, and answer “yes” or “no” to the question: “Do you consider that there is a reasonable possibility that the event may have been caused by the MEDI-573?”

For SAEs, a causal relationship will also be assessed for any other medication and study procedure. Note that for SAEs that could be associated with any study procedure the causal relationship is implied as “yes”.

A guide to the interpretation of the causality question is found in Appendix B of this Clinical Study Protocol.

### **Adverse events based on signs and symptoms**

All AEs spontaneously reported by the subject or reported in response to the open question from the study personnel: “Have you had any health problems since the previous visit/you were last asked?” or revealed by observation will be collected and recorded in the CRF. When collecting AEs, the recording of diagnoses is preferred (when possible) to recording a list of signs and symptoms. However, if a diagnosis is known and there are other signs or symptoms that are not generally part of the diagnosis, the diagnosis and each sign or symptom will be recorded separately.

### **Adverse events based on examinations and tests**

The results from protocol mandated laboratory tests, vital signs, ECGs and other safety assessments will be summarised in the Clinical Study Report. Deterioration as compared to baseline in these parameters will therefore only be reported as AEs if they fulfil any of the criteria for a SAE or DLT, or are the reason for discontinuation of treatment with the investigational product unless clearly due to progression of disease under study (see Disease progression).

If deterioration in a laboratory value, vital sign, ECG or other safety assessment is associated with clinical signs and symptoms, the sign or symptom will be reported as an AE and the associated laboratory result or other finding will be considered as additional information.

Date

Wherever possible the reporting investigator uses the clinical, rather than the laboratory term (eg, anaemia versus low haemoglobin value).

Deterioration of a laboratory value that is unequivocally due to disease progression should not be reported as an AE.

Any new or aggravated clinically relevant abnormal medical finding at a physical examination as compared with the baseline assessment will be reported as an AE.

### **Disease progression**

Disease progression can be considered as a worsening of a subject's condition attributable to the disease for which the investigational product is being studied. It may be an increase in the severity of the disease under study and/or increases in the symptoms of the disease. The development of new, or progression of existing metastasis to the primary cancer under study should be considered as disease progression and not an AE. Events that are unequivocally due to disease progression should not be reported as AEs during the study.

### **New cancers**

The development of a new cancer should be regarded as an AE and will generally meet at least one of the serious criteria. New cancers are those that are not the primary reason for the administration of the study treatment and have been identified after the subject's inclusion in this study. They do not include metastases of the original cancer.

### **Handling of deaths**

All deaths that occur during the study, or until 30 days after the last dose of MEDI-573, should be reported as follows:

- Death, which is unequivocally due to disease progression, should be communicated to the study monitor at the next monitoring visit and should be documented in the CRF module, but should not be reported as a SAE during the study
- Where death is not clearly due to disease progression of the disease under study the AE causing the death should be reported to the study monitor as an SAE within 1 day. The report should contain a comment regarding the co-involvement of progression of disease, if appropriate, and should assign a single primary cause of death together with any contributory causes
- Deaths with an unknown cause should always be reported as a SAE but every effort should be made to establish a cause of death. A post-mortem may be helpful in the assessment of the cause of death, and if performed a copy of the post-mortem results (with translation of important parts into English) should be reported in an expedited fashion to an AstraZeneca representative within the usual timeframes.

Date

#### **6.4.4 Reporting of serious adverse events**

All SAEs have to be reported, whether or not considered causally related to the investigational product, or to the study procedure(s). All SAEs occurred after informed consent will be recorded in the CRF.

Investigators and other site personnel should inform (emergency report) appropriate AstraZeneca representatives of any SAE that occurs at his or her site in the course of the study within 1 day (in this section, within 1 day is defined as “immediately but no later than the end of the next business day”) of when he or she becomes aware of it (initial SAE report). This should apply whether or not the SAE is considered causally related to the study treatment or to the study procedure(s). The Principal Investigator should provide detailed information to AstraZeneca in writing **within 4 calendar days** of the initial report. The Principal Investigator should notify the SAEs in writing to the head of the study site immediately.

Follow-up information on SAEs should also be reported to AstraZeneca by the investigator(s) within the same time frames. If a non-serious AE becomes serious, this and other relevant follow-up information should also be provided to AstraZeneca within 1 day as described above.

The following information is required in the initial SAE report to AstraZeneca from the investigator(s): study code, site number, SID, AE, seriousness, start date.

The following detailed information should be sent to AstraZeneca as soon as it becomes available: severity, outcome (including stop date, if available), causality (investigational product and if applicable any other concomitant drug), date when a non-serious AE became serious, withdrawal of study treatment, treatment of AE, concurrent therapy (except for treatment of AE), concurrent medication (including pre-study medication if the causality of the AE cannot be assessed), date of birth, sex, other current illnesses, relevant medical history and if applicable, date and course of death.

The Head of the study site should submit a written report to the Institutional Review Board providing the details of all AE case(s) reported by AstraZeneca.

### **6.5 Pharmacokinetics**

#### **6.5.1 Collection of pharmacokinetic samples**

Blood samples for assessment of PK parameters of MEDI-573 and for immunogenicity of anti-MEDI-573 antibodies will be collected as described in [Table 5](#), [Table 9](#), [Table 13](#), and [Table 14](#).

Date

**Table 13**                      **Pharmacokinetic and Pharmacodynamics (Cohorts 1 and 2)**

Time for blood samples			PK	Biomarkers	
			573	antibodies	
Cycle 1	Day 1	Pre-dose	X	X	X
		End of infusion (+5 min)	X		X
		2 h after dose ( $\pm 15$ min)	X		X
		6 h after dose ( $\pm 15$ min)	X		X
	Day 2	24 h after dose of Day 1 ( $\pm 2$ h)	X		X
	Day 3	48 h after dose of Day 1 ( $\pm 2$ h)	X		X
	Day 8	Pre-dose	X		X
		End of infusion (+5 min)	X		X
	Day 15	Pre-dose	X		X
		End of infusion (+5 min)	X		X
Cycle 2	Day 1	Pre-dose	X	X	X
		End of infusion (+5 min)	X		X
	Day 8	Pre-dose	X		X
		End of infusion (+5 min)	X		X
	Day 15	Pre-dose	X		X
		End of infusion (+5 min)	X		X
Cycle 3 and beyond	Day 1	Pre-dose	X	X	X
		End of infusion (+5 min)	X		X
End of treatment			X		X
30 days after the last dose			X	X	X
3 months after the last dose				X	

Date

**Table 14 Pharmacokinetic and Pharmacodynamics (Cohort 3)**

Time for blood samples			PK	Biomarkers	
			573 antibodies		
Cycle 1	Day 1	Pre-dose	X	X	X
		End of infusion (+5 min)	X		X
		2 h after dose ( $\pm 15$ min)	X		X
		6 h after dose ( $\pm 15$ min)	X		X
	Day 2	24 h after dose of Day 1 ( $\pm 2$ h)	X		X
	Day 3	48 h after dose of Day 1 ( $\pm 2$ h)	X		X
	Day 8	168 h after dose of Day 1 ( $\pm 2$ h)	X		X
	Cycle 2 and beyond	Day 1	Pre-dose	X	X
End of infusion(+5 min)			X		X
End of treatment			X		X
30 days after the last dose			X	X	X
3 months after the last dose				X	

The timing of the PK samples may be adjusted during the study, dependent on emerging data, in order to ensure appropriate characterisation of the plasma concentration-time profiles. The total number of samples and the total volume of blood taken from each subject will not exceed that presented in Section 6.8.1.

Collection, labelling, storage and shipment of the samples will be done in accordance with the Laboratory Manual.

### 6.5.2 Determination of drug concentration in pharmacokinetic samples

Samples for determination of MEDI-573 concentrations in serum will be analysed by the central laboratory of AstraZeneca, using an appropriate bioanalytical method. Full details of the analytical method used will be described in a separate bioanalytical report.

All samples still within the known stability of the analytes of interest (ie, *MEDI-573*) at the time of receipt by the bioanalytical laboratory will be analysed.

### 6.5.3 Immunogenicity

Anti-MEDI-573 antibodies will be measured at the visits indicated in the Study Plan (Table 5 and Table 9). If sample of anti-MEDI-573 antibodies is collected on treatment day, it should be collected prior to infusion. The date and time of collection of each sample will be recorded. Samples will be analysed by the central laboratory of AstraZeneca.

Date

Further details on sample processing, handling and shipment are provided in the Laboratory Manual.

## **6.6 Pharmacodynamics**

Samples for biomarker analysis and other biological process evaluation will be collected as indicated in the Study Plan ([Table 5](#) and [Table 9](#)). Specific biomarkers will include free and bound IGF-I and IGF-II. See [Table 15](#) for institutions responsible for each measurement.

## **6.7 Exploratory research**

### **6.7.1 Exploratory biomarker research**

If a subject agrees to participate in the exploratory biomarker research component of the study biological samples (eg, plasma, serum, archived and study-obtained tumour, etc) will be collected and may be analysed for exploratory biomarkers to assess correlations with disease activity, effects of investigational product and clinical outcomes.

The results of this exploratory biomarker research will be reported separately and will not form part of the Clinical Study Report.

The results of this exploratory biomarker research may be pooled with biomarker data from other studies with the investigational product to generate hypotheses to be tested in future studies.

#### **6.7.1.1 Collection of archival tumour samples**

The effects of genetic variation and expression levels of IGF-IR, IRS-1, MAPK, IR, antigen identified by monoclonal antibody Ki67, caspase 3, and/or AKT will be investigated and their association with treatment with MEDI-573 and clinical outcome will be evaluated when tumour samples are available. And, cell mortality will be assessed by TUNEL. All subjects will be asked to provide consent to supply a sample of their archival tumour blocks if a sample taken at the time of diagnosis is available. No further biopsy procedures are required.

Further details on sample processing, handling and shipment are provided in the Laboratory Manual.

#### **6.7.1.2 Collection of exploratory blood-borne biomarkers**

##### **Exploratory biomarker research samples**

Blood collection for assessment of biomarkers and other biological processes will be performed as described in [Table 5](#) and [Table 9](#). See [Table 15](#) for specific biomarkers and institutions responsible for each measurement.

Details on sample processing, handling, shipment and storage are provided in the Laboratory Manual.

Date

**Table 15**                      **Specific biomarkers**

Institution	Specific biomarker
central laboratory of Sponsor	free IGF-I and IGF-II bound IGF-I and IGF-II IGFBPs
clinical laboratory	GH insulin glucose Underlying disease-specific tumour marker (when appropriate, such as prostate specific antigen [PSA] and cancer antigen 125 [CA 125])

## **6.7.2 Pharmacogenetics**

Fresh and /or archival tumour samples will be collected, provided that separate written consent on pharmacogenetics. Tumour samples will be used to analyze the effects of MEDI-573 on levels of mRNA genes. The relationship of IGF pathway-related components at the mRNA level, including IR-A mRNA level (IGF-I, IGF-II, INSR, IR-B, IR-A, IGF-IR, IGF-IIR, IRS-1, IRS-2, IGFBP-1, IGFBP-2, IGFBP-3, IGFBP-4, IGFBP-5, IGFBP-6) in tumour biopsies obtained pre- and post-MEDI-573 treatment will be evaluated with qRT-PCR assays or microarray studies. The results of this pharmacogenetic research will be reported separately and will not form part of the Clinical Study Report.

### **6.7.2.1 Collection of pharmacogenetic samples**

Samples will be analysed by the central laboratory of AstraZeneca.

Details on sample processing, handling, shipment and storage are provided in the Laboratory Manual.

## **6.8 Biological sampling procedures**

### **6.8.1 Volume of blood**

The total volume of blood that will be drawn from each subject at screening and during Cycle 1 in this study is shown in [Table 16](#).

Date

**Table 16** Volume of blood to be drawn from each subject during Cycle 1 (including screening period)

		Sample volume (mL)	Number of samples	Total volume (mL)
Safety	Clinical Chemistry	5	5 (4 a )	25 (20 a )
	Haematology	2.6	5 (4 a )	13 (10.4 a )
PK	MEDI-573	4	10 (7 a )	40 (28 a )
IM	Anti-MEDI-573 antibodies	8.5	1	8.5
Exploratory biomarker research	Central laboratory of Sponsor	16	10 (7 a )	160 (112 a )
Soluble protein	Clinical laboratory	5	10 (7 a )	50 (35 a )
Tumour markers b		3.5	1	3.5
TOTAL				300 (217.4a)

a Cohort 3

b Depend on target tumours

The total volume of blood that will be drawn from each subject at cycle 2 in this study is shown in [Table 17](#).

**Table 17** Volume of blood to be drawn from each subject during Cycle 2

		Sample volume (mL)	Number of samples	Total volume (mL)
Safety	Clinical Chemistry	5	3 (2 a )	15 (10 a )
	Haematology	2.6	3 (2 a )	7.8 (5.2 a )
PK	MEDI-573	4	6 (2 a )	24 (8 a )
IM	Anti-MEDI-573 antibodies	8.5	1	8.5
Exploratory biomarker research	Central laboratory of Sponsor	16	6 (2 a )	96 (32 a )
Soluble protein	Clinical laboratory	5	6 (2 a )	30 (10 a )
TOTAL				181.3 (73.7a)

a Cohort 3

b Depend on target tumours

The total volume of blood that will be drawn from each subject at Cycle 3 and beyond in this study is shown in [Table 18](#).

Date

**Table 18** Volume of blood to be drawn from each subject during Cycle 3 and beyond

		Sample volume (mL)	Number of samples	Total volume (mL)
Safety	Clinical Chemistry	5	3 (2 a )	15 (10 a )
	Haematology	2.6	3 (2 a )	7.8 (5.2 a )
PK	MEDI-573	4	2	8
IM	Anti-MEDI-573 antibodies	8.5	1	8.5
Exploratory biomarker research	Central laboratory of Sponsor	16	2	32
Soluble protein	Clinical laboratory	5	2	10
Tumour markers b		3.5	1	3.5
TOTAL				84.8 (77.2a)

a Cohort 3

b Depend on target tumours and only on Day 1 of odd cycles (pre-dose)

The total volume of blood that will be drawn from each subject at treatment discontinuation and during the follow-up in this study is shown in [Table 19](#).

**Table 19** Volume of blood to be drawn from each subject at the end of treatment, 30 days and 3 months follow-up

		Sample volume (mL)	Number of samples	Total volume (mL)
Safety	Clinical Chemistry	5	2	10
	Haematology	2.6	2	5.2
PK	MEDI-573	4	2	8
IM	Anti-MEDI-573 antibodies	8.5	2	17
Exploratory biomarker research	Central laboratory of Sponsor	16	2	32
Soluble protein	Clinical laboratory	5	2	10
Tumour markers a		3.5	2	7
TOTAL				89.2

a Depend on target tumours

Date

## **6.8.2 Handling, storage and destruction of biological samples**

The samples will be used up, or disposed of after analyses or retained for further use as described below.

Biological samples for future research will be retained at the central laboratory of AstraZeneca for a maximum of 15 years following the last subject's last visit in the study.

The results from future analysis will not be reported in the Clinical Study Report but separately in a Clinical Study Report Addendum /Scientific Report or Scientific Publication.

### **6.8.2.1 Pharmacokinetic samples**

Incurred sample reproducibility analysis, if any, will be performed alongside the bioanalysis of the test samples and reported in a separate bioanalytical report.

### **6.8.2.2 Samples for exploratory research**

Details on sample processing, handling, shipment and storage are provided in the Laboratory Manual.

For exploratory analyses, all collected specimens are identified on the sample itself by study number and alphanumeric number. Collection kits are supplied for each subjects visit and sample type. Alphanumeric numbers are pre-assigned to those kits. There are no personal identifiers associated with the sample tube. Samples are stored in this manner.

Should a withdrawal of consent occur, the participant is to notify the collection personnel which in turn would notify the proper individuals in Japan and then the information is passed to MedImmune. The samples are then destroyed. It is important to note that if data has been obtained prior to the request, that data can still be used. Chain of custody is maintained via inventory during the shipping process and upon receipt at MedImmune where the samples are verified and entered into a relational database and all movements are tracked. All of our samples are stored within an access restricted area.

## **6.8.3 Labelling and shipment of biohazard samples**

The Principal Investigator ensures that samples are labelled and shipped in accordance with the Laboratory Manual and the Biological Substance, Category B (materials containing or suspected to contain infectious substances that do not meet Category A criteria), see Appendix C of this Clinical Study Protocol 'IATA 6.2 Guidance Document'.

Any samples identified as Infectious Category A materials are not shipped and no further samples taken from the subject unless agreed with AstraZeneca and appropriate labelling, shipment and containment provisions are approved.

All archival tumour samples should be shipped at ambient temperature as per the Laboratory Manual to the central laboratory of AstraZeneca.

Date

#### **6.8.4 Chain of custody of biological samples**

A full chain of custody is maintained for all samples throughout their lifecycle.

The Principal Investigator keeps full traceability of collected biological samples from the subjects while in storage at the centre until shipment or disposal (where appropriate) and keeps documentation.

The sample receiver keeps full traceability of the samples while in storage and during use until used or disposed of.

AstraZeneca keeps oversight of the entire life cycle through internal procedures, monitoring of study sites and auditing of external laboratory providers.

Samples retained for further use are registered in the AstraZeneca biobank system during the entire life cycle.

#### **6.8.5 Withdrawal of informed consent for donated biological samples**

If a subject withdraws consent to the use of voluntarily donated biological samples, then the samples will be disposed of/destroyed, and the action will be documented. If samples are already analysed, AstraZeneca is not obliged to destroy the results of this research.

If collection of biological samples is a voluntary part of the study include:

As collection of these biological samples is a voluntary part of the study then the subject may continue in the study.

If collection of any biological samples is a mandatory part of the study include:

As collection of the biological samples is an integral part of the study, then the subject is withdrawn from further participation in the study.

The Principal Investigator:

- Ensures AstraZeneca is notified immediately of the subject's withdrawal of informed consent to the use of donated biological samples
- Ensures that biological samples from that subject, if stored at the study site, are immediately identified, disposed of/destroyed, and the action is documented
- Ensures the laboratory(ies) holding the samples is/are informed about the withdrawn consent immediately and that samples are disposed of/destroyed, the action is documented and the signed document is returned to the study site
- Ensures that the subject and AstraZeneca are informed about the sample disposal

Date

AstraZeneca ensures the central laboratory(ies) holding the samples is/are informed about the withdrawn consent immediately and that samples are disposed of/destroyed, the action is documented and the document is returned to the study site.

## **6.9 Anti-tumour activity**

### **6.9.1 Tumour assessments**

Tumour response will be assessed in all subjects with measurable and/or non-measurable disease at baseline.

RECIST ver1.1 will be used for measurable, non-measurable, target lesions and non-target lesions and the objective tumour response criteria in this study.

The preferred methods of assessment are CT or MRI performed on anatomical coverage to adequately define all areas of disease at baseline.

Baseline tumour assessments should be performed no more than 28 days before the start of study treatment. Following the baseline assessment, tumour burden will be assessed for all subjects by RECIST ver1.1 after start of study treatment (see [Table 5](#) and [Table 9](#)) until discontinuation of study treatment (subjects who discontinue the study treatment for reasons other than disease progression or initiation of alternative anticancer therapy will undergo Tumour assessment 3 months after the last dose of MEDI-573) or withdrawal of consent. The same methods of assessment and the same anatomical coverage should be used as per baseline at each subsequent follow-up assessment. Any other sites at which new disease is suspected should also be imaged appropriately.

If the investigator is in doubt as to whether progression has occurred, particularly with response to non-target lesions or the appearance of a new lesion, it is advisable to continue treatment and reassess the subject's status at the next scheduled assessment or sooner if clinically required.

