#### **Subject Evaluation/Follow-up**

A schedule of screening, treatment visit and follow-up visit procedures are presented in [Table 5](#) (Cohorts 1 and 2) and [Table 9](#) (Cohort 3).

The details of the evaluations are shown in Section 6.1.

[figure not shown]
AEs and SAEs during the study will be assessed from the time the subject provides the consent through 30 days after the last dose of MEDI-573. AEs will be graded according to the National Cancer Institute Common Terminology Criteria for Adverse Events Version 4.0 (NCI CTCAE V4.0). In addition, disease evaluations (including computerised tomography (CT) or magnetic resonance imaging (MRI) scans), focused physical examination, and world health organization (WHO) performance status will be performed after every 2 cycles of treatment until documentation of disease progression or initiation of alternative anticancer therapy. For subjects who discontinue treatment due to reasons other than disease progression or initiation

Date

of alternative anticancer therapy, disease evaluations will be performed at 3 months after the last dose of MEDI-573. Subjects will be evaluated for disease response using Response Evaluation Criteria in Solid Tumours (RECIST ver 1.1; [Eisenhauera et al 2009](#)).

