#### 4.3.1 Concomitant treatments

All concomitant medications used by the subject from the time the subject signs the informed consent form through 30 days after the last dose of MEDI-573 will be recorded on source documentation.

Subjects may receive medications to treat AEs as deemed necessary by the investigators.

Any anticancer drug is not allowed during study.

Pre-medication will be allowed after, but not before the first dose of study treatment. This includes management of diarrhoea, nausea and vomiting.

Diphenhydramine and acetaminophen, or the institutional equivalents, may be administered for treatment of an infusion reaction during infusion or prophylactic administration for subjects who experience an infusion reaction. If Grade 2 or Grade 3 infusion reaction occurs and steroid is considered preferable to acetaminophen and diphenhydramine, steroid may be administered at the investigator's decision.

The routine use of ESAs and colony stimulating factors is not allowed. Use of such agents in the first cycle will require replacement of the subject in that cohort.

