## **7.7 Calculation or derivation of tumour response variables**

The preliminary anti-tumour activity of MEDI-573 will be assessed based on the following variables: objective response rate (ORR), time to response (TTR), duration of response (DR), time to progression (TTP), and progression-free survival (PFS).

Categorisation of overall objective tumour response assessment will be based on the RECIST ver1.1: complete response (CR), partial response (PR), stable disease (SD) and progressive disease (PD) for all subjects with measurable disease at entry.

Response will be calculated in comparison to the baseline tumour measurements obtained before starting study treatment. Progression will be calculated in comparison to when the tumour burden was at a minimum (ie, smallest sum of diameters previously recorded since starting the study).

For patients that have measurable disease at entry, overall response at entry will be determined programmatically by the measurement of the target lesion, the response of the non-target

Date

lesion and the presence of new lesion according to the RECIST ver1.1. The subject's best overall response is the best response recorded from the start of the study treatment.

In the case of SD, measurements should have met the SD criteria at least once after the study start. To be assigned a status of partial response or complete response, changes in tumour assessments should be confirmed no less than 4 weeks after the criteria for response were first met.

For subjects that only have non-measurable disease at study entry, RECIST will be used. Visit response will be assigned programmatically and summarised separately.

Percentage change in tumour size will be determined by the percentage change in the sum of the longest diameters of target lesions.

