### **7.7.1 Objective response and disease control**

ORR is defined as the proportion of subjects with confirmed CR or confirmed PR according to RECIST ver1.1. Confirmed responses are those that persist on repeat imaging study  $\geq 4$  weeks after the initial documentation of response.

TTR will be measured from the start of treatment with MEDI-573 to the first documentation of objective response and will only be assessed in subjects who have achieved objective response.

DR will be defined as the duration from the first documentation of objective response to the first documented disease progression. DR will only be calculated for the subgroup of subjects with an objective response during the study period (until 3 months after the last dose).

TTP will be measured from the start of treatment with MEDI-573 until the documentation of disease progression during the study period (until 3 months after the last dose).

PFS will be measured from the start of treatment with MEDI-573 until the documentation of disease progression or death due to any cause, whichever occurs first during the study period (until 3 months after the last dose).

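### The 3-month tumour assessment depends only on why MEDI-573 was stopped, and no record of new anticancer therapy is required after day 30, so scans taken under another therapy can enter TTP, PFS and DR

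*Protocol*

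**What the plan says.** **The 3-month scan.** Section 6.9.1 sets the rule by reason for stopping: "subjects who discontinue the study treatment for reasons other than disease progression or initiation of alternative anticancer therapy will undergo Tumour assessment 3 months", counted from the final dose. Section 3.1 does the same for subjects who stop for reasons other than progression or initiation "of alternative anticancer therapy, disease evaluations will be performed at 3 months after the last dose of MEDI-573". Footnote e of Tables 5 and 9 repeats it.

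**The on-treatment scans.** Section 3.1 places these "after every 2 cycles of treatment until documentation of disease progression or initiation of alternative anticancer therapy".

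**The endpoints.** Section 7.7.1 takes PFS to "documentation of disease progression or death due to any cause, whichever occurs first during the study period (until 3 months after the last dose"). TTP has the same window, and DR is calculated for responses within it. Section 7.7 says that the "best overall response is the best response recorded from the start of the study treatment", with no stated end. None of these definitions refers to the start of another anticancer treatment.

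**What is recorded.** Section 4.3.1 says that concomitant medications from consent "through 30 days after the last dose of MEDI-573 will be recorded on source documentation". The Concomitant Medications row of Tables 5 and 9 has an entry at the 30-day visit and none at the 3-month visit. Section 6.3.6 asks about medications at 30 days and describes the 3-month visit only in terms of immunogenicity and anti-tumour activity.

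**The restriction.** Section 4.3.1 also says: "Any anticancer drug is not allowed during study".

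**The concern.** Consider a subject with stable disease who stops MEDI-573 for an adverse event and starts another therapy six weeks after the last dose. The reason for stopping was neither progression nor new therapy, so the 3-month scan is due. If the new therapy holds the tumour, the progression-free time is carried to month 3 and credited to MEDI-573. If the tumour grows, the progression is also attributed to MEDI-573.

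Observing anti-tumour activity is a secondary objective, and with a single arm there is no comparison group in which such contamination would show. The usual remedy is to leave out assessments made after new therapy begins. That needs a start date, and the protocol does not require one for therapy begun after day 30.

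**Working it through.** **1. Does any rule keep the scan out?** The places that could do so, set side by side:

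- 3.1 (3-month sentence), 6.9.1 and footnote e: the trigger is the reason for stopping. Therapy started after stopping is not considered.
- 3.1 (on-treatment sentence): new therapy ends evaluation, but the limit is attached to the scans after every two cycles and is not carried over to the 3-month scan.
- 4.3.1: the restriction is worded for the study as a whole. Section 4.3 applies its restrictions during treatment and for specified times before and after, and no such time is given for anticancer drugs. Section 5.4.1 says that subjects who stop MEDI-573 permanently leave the study, whereas 7.7.1 extends the study period to 3 months after the last dose. The restriction therefore does not clearly reach the follow-up.

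No rule clearly does so.

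**2. Which results can the scan enter?**

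- TTP, PFS and DR: directly, because their windows run to 3 months.
- Percentage change in tumour size and a best response of SD: directly, because no cut-off is stated.
- Confirmed CR or PR: only if the response was first seen by end of treatment. Confirmation needs repeat imaging at least 4 weeks later, and no scan is scheduled after month 3.

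**3. How long is the unrecorded period?** Inputs: recording ends at day 30 (visit window +3 days); the 3-month visit has a window of ±14 days (Tables 5 and 9). Assumption: 3 months = 91 days.

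- Nominal: 91 − 30 = 61 days, and 61 / 91 = 67% of the post-treatment period.
- Shortest: (91 − 14) − (30 + 3) = 77 − 33 = 44 days.
- Longest: (91 + 14) − 30 = 105 − 30 = 75 days.

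Taking 3 months as 90 or 92 days gives 60 (43 to 74) or 62 (45 to 76) days.

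**4. How much weight has one subject?** The planned size reproduces: 3 cohorts × 3 = 9 and 3 × 6 = 18 evaluable subjects. One subject is 1/18 = 5.6%, 1/9 = 11.1%, 1/6 = 16.7% or 1/3 = 33.3% of the study or cohort. These are weights, not expected biases.

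**5. How likely is at least one affected subject?** The protocol gives no rate. If a share *q* of subjects starts new therapy after day 30 and is still scanned, the chance of at least one is 1 − (1 − *q*)^*n*. For assumed *q* from 5% to 30%:

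- *n* = 9: 1 − 0.95^9 = 37% to 1 − 0.70^9 = 96%.
- *n* = 18: 1 − 0.95^18 = 60% to 1 − 0.70^18 = 99.8%.

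The range only illustrates how the chance depends on *q*. The argument does not rest on it.

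**The case against.** Several counter-arguments have weight.

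- *Anticancer drugs are already disallowed.* If the 4.3.1 restriction is read together with the 7.7.1 study period, next-line drug therapy before month 3 is not permitted. That reading is possible, but 4.3 and 5.4.1 point the other way, so the passages need reconciling. Even on this reading, nothing required after day 30 would show whether the restriction was kept.
- *Censoring rules belong in the analysis plan.* This stands. The absence of a censoring rule here is not itself the finding. The scan trigger and the end of recording are fixed in the protocol.
- *The CRF may ask about later therapy anyway.* It may; it is not shown. The claim is therefore limited: the protocol does not require the date. A reader might infer that no analysis plan could ever exclude these scans, but the documents do not establish that. Therapy started within 30 days is in any case recorded.
- *Response rate is hardly touched.* A reader might infer that a response produced by another drug could raise a cohort's ORR by 17 to 33 percentage points. A response first seen at month 3 has no later scheduled scan to confirm it, so the route is narrow.
- *Section 3.1 does not contradict itself.* A reader might see a conflict between its two sentences. The limit on new therapy belongs to the two-cycle scans, so this is an inconsistent treatment of new therapy rather than a contradiction.
- *Deaths after new therapy count as PFS events.* This is a conventional choice and not an error.

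The endpoints are also preliminary and descriptive, and subjects whose disease is refractory or has no standard therapy may have few further options.

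**Conclusion.** The point holds in a limited form. The 3-month scan is required whatever therapy has started since MEDI-573 was stopped, and it can enter TTP, PFS and DR. It can also affect percentage change in tumour size, a best response of SD and, narrowly, confirmation of an earlier response. For about two thirds of the post-treatment period (61 of 91 days; 44 to 75 days with visit windows) there is no required record of new therapy.

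This rests on taking 3 months as 91 days and on reading the 4.3.1 restriction as not clearly reaching the follow-up. How many subjects would be affected is unknown.

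A reader might extend the point to safety or dose selection. The documents do not support that: the primary safety objective does not use this scan, and DLTs are assessed in Cycle 1. The change is worth making because it is cheap and protects a stated secondary objective, but the study does not depend on it.

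**What to change.** 1. In 4.3.1 and in Tables 5 and 9, require the type and start date of any subsequent anticancer treatment, including radiotherapy or surgery, to be recorded in the CRF through the existing 3-month visit.
2. In 3.1, 6.9.1 and footnote e of Tables 5 and 9, limit the 3-month tumour assessment to subjects who have neither progressed nor started other anticancer treatment by then, in line with the limit that 3.1 already puts on the two-cycle scans.
3. In 7.7 and 7.7.1, state that tumour assessments after the start of other anticancer treatment do not count for best response, confirmation, DR, TTP or progression in PFS.
4. Reconcile the terms: 4.3.1 speaks of drugs and of the study, 5.4.1 of alternative therapy and of leaving the study, and 7.7.1 of a study period to 3 months. This is a matter of consistent wording and does not call for a new clinical rule on which treatments are permitted.

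The cost is one CRF item at an existing visit, wording changes and slightly more censoring. No visits or subjects are added.
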